### 5 Study Design

The study shall be a prospective, single arm, multicenter study. Endoscopists comprising a range of clinical experience will be invited to participate in the study at each site. All

participating endoscopists will receive an overview of the NICE classification to guide their unaided and CDSD-aided assessments as well as instruction on the use of CDSD.

For each participating endoscopist, consecutive subjects presenting for colonoscopy and meeting the pre-procedure entrance criteria will be consented and screened. Consented subjects meeting all the entrance criteria will be enrolled and undergo colonoscopy per the standard of care with the added use of CDSD. CDSD-unaided and CDSD-aided predictions will be compared with the ground truth of histopathology. Presuming at least 40 endoscopists participate, each endoscopist will make approximately 60 predictions on diminutive polyps through the course of the study.

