### 5.3 *Justification for the Study Design*

This study design was chosen to follow current standard of care endoscopy procedures with the exception of introduction of CDSD as part of the physician's decision algorithm. Pathology remains the gold standard methodology for diagnosis in this study. The study aims to demonstrate that CDSD is capable of increasing the sensitivity and specificity of endoscopist predictions for diminutive polyp histology. The single arm design was chosen to evaluate the incremental improvement in predictive accuracy relative to the standard of care while controlling for variability in polyp presentation by using a matched pair design. Inclusion of endoscopists comprising a range of experience is intended to reflect real-life clinical practice and potential increased benefit to non-expert users. Blinding allows for independence of assessments, and comparison of results without bias.

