#### 9.1.1.3 Statistical Methods

The 95% confidence intervals for the differences between CDSD-aided and CDSD-unaided sensitivity and specificity are estimated using bootstrap resampling with resampling performed first at the endoscopist level and then at the patient level. The null hypothesis is rejected if both lower bounds of the confidence intervals are greater than 0.

$$Sn_{CDSD\text{-aided}} - Sn_{CDSD\text{-unaided}} > 0$$

$$Sp_{CDSD\text{-aided}} - Sp_{CDSD\text{-unaided}} > 0$$

The assumptions of the statistical model used to establish the sample size are:

1. There are at a minimum 40 endoscopists participating in the study and each endoscopist makes approximately 60 predictions,
2. For each endoscope (CF-HQ190 and PCF-H190) and for each class of diminutive polyp (adenoma and non-adenoma) there is an intra-cluster correlation coefficient of 0.05 for predictions made by the same endoscopist,
3. There is no correlation between an operator's sensitivity and specificity,
4. There is no correlation between predictions made by the same operator across endoscope models (CF-HQ190 and PCF-H190),
5. The distribution of adenomas and non-adenomas within subjects with more than one diminutive polyp was modelled and is described in the statistical analysis plan,
6. The values from the range of possible values for the discordant pairs (b, c, n and p) that are used to calculate sample size are reported in Tables 9-3, 9-4, 9-5 and 9-6),
7. Without CDSD, the operator sensitivity is presumed to be 88% and the specificity is presumed to be 58% across all operators for all colonoscopes. The operator sensitivity with CDSD is presumed to be 92% and specificity with CDSD is presumed to be 75% across all operators when using the CF-HQ190 colonoscope (benchtop testing data). The operator sensitivity with CDSD is presumed to be 91% and the specificity with CDSD is presumed to be 72% across all operators when using the PCF-H190 colonoscope (benchtop testing data). Combined, the operator

sensitivity with CDSD is presumed to be 92% and the specificity with CDSD is presumed to be 73% across all operators,

8. The prediction rate for CDSD with CF-HQ190 is 89% and the prediction rate for CDSD with the PCF-H190 is 84% (benchtop testing data),
9. The proportion of subjects examined with the PCF-H190 will be 50%,

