10. The proportion of subjects that present with adequate bowel preparation will be 85%, the proportion of patients with diminutive polyps will be 52%, there will be 1.81 diminutive polyps per subject having diminutive polyps, the overall prevalence of adenomas will be 58%,
11. The proportion of predictions with and without CDSD that will be assessed as normal tissue by pathology is estimated to be approximately 15%.

A simulation analysis was performed in which a dataset is generated at each step following the assumptions above. To account for intra-cluster correlation at the endoscopist level, for each endoscope and each class of diminutive polyps, the proportions of accurate and non-accurate predictions are sampled following a Dirichlet distribution, as described in Gönen. At each simulation step, bootstrap resampling based 95% confidence intervals for the differences between CDSD-aided and CDSD-unaided sensitivity and specificity are calculated. Bootstrap resampling is performed first at the endoscopist level and then at the patient level. The power is calculated as the number of simulation steps where the lower bound of both confidence intervals is greater than 0.

**Table 9-3: Assumptions for Proportions of Predictions for Adenomas (Sensitivity, Reference Standard Positive) with CF-HQ190**

		CDSD-unaided Prediction		Total
		Positive	Negative	
CDSD-aided Prediction	Positive	0.8411	0.0859	0.9270
	Negative	0.0365	0.0365	0.073
	Total	0.8776	0.1224	1.00

**Table 9-4: Assumptions for Proportions of Predictions for Adenomas (Sensitivity, Reference Standard Positive) with PCF-H190**

		CDSD-unaided Prediction		Total
		Positive	Negative	
CDSD-aided Prediction	Positive	0.8301	0.0749	0.905
	Negative	0.0475	0.0475	0.095
	Total	0.8776	0.1224	1.00

**Table 9-5: Assumptions for Proportions of Predictions for Non-Adenomas (Specificity, Reference Standard Negative) with CF-HQ190**

		CDSUnaided Prediction		Total
		Positive	Negative	
CDSD-aided Prediction	Positive	0.124	0.124	0.248
	Negative	0.299	0.453	0.752
	Total	0.423	0.577	1.00

**Table 9-6: Assumptions for Proportions of Predictions for Non-Adenomas (Specificity, Reference Standard Negative) with PCF-H190**

		CDSUnaided Prediction		Total
		Positive	Negative	
CDSD-aided Prediction	Positive	0.1415	0.1415	0.283
	Negative	0.2815	0.4355	0.717
	Total	0.423	0.577	1.00

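### The stated 80% power does not follow from the plan's own inputs and its endoscopist-then-patient bootstrap, which give about 64 to 67% at 1,918 polyps and 73 to 77% at 2,400

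*Combined protocol and SAP*

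**What the plan says.** Section 9.1.1.2 and the synopsis claim 80% power at one-sided 2.5% with 40 endoscopists, about 2,400 subjects and 1,918 polyps. Section 9.1.1.3 attributes the figure to a simulation.

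- **Data model.** "for each endoscope and each class of diminutive polyps, the proportions of accurate and non-accurate predictions are sampled following a Dirichlet distribution". Assumption 2 adds that, for each endoscope and polyp class, "there is an intra-cluster correlation coefficient of 0.05 for predictions made by the same endoscopist". Assumption 4 states: "There is no correlation between predictions made by the same operator across endoscope models (CF-HQ190 and PCF-H190".
- **Test.** "Bootstrap resampling is performed first at the endoscopist level and then at the patient level". Success requires both lower 95% limits, for the sensitivity and the specificity difference, to exceed 0. The text does not say how patients are redrawn at the second stage.
- **Cluster size.** Section 5 says "each endoscopist will make approximately 60 predictions on diminutive polyps through the course of the study", and assumption 1 repeats this.
- **Scope mix.** Assumption 9 says "The proportion of subjects examined with the PCF-H190 will be 50"%. This is a study-level share; no mix per endoscopist is given.
- **No-prediction polyps.** Assumption 8 says "The prediction rate for CDSD with CF-HQ190 is 89"%, with 84% for the PCF-H190. The text does not say whether Tables 9-3 to 9-6 already allow for this.

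**The concern.** The power figure is the only stated justification for 40 endoscopists and 2,400 subjects, and the co-primary objective fails if sensitivity alone misses. Three features of the calculation raise doubt.

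First, a bootstrap that redraws endoscopists and then redraws patients within them counts the within-endoscopist variation twice: it is already present in the spread of the endoscopist means. The interval is then wider than the true sampling error warrants, and power falls. The stated 80% lies close to what an endoscopist-only bootstrap would give.

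Second, 60 predictions for each of 40 endoscopists is 2,400 polyps, not 1,918. The number 60 equals subjects per endoscopist (2,400/40), so it may be a slip, but the documents do not say.

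Third, zero is the most favourable non-negative value for the cross-scope correlation. Section 5.3 describes the range of endoscopist experience as "intended to reflect real-life clinical practice and potential increased benefit to non-expert users". A benefit that depends on the person could follow that person from one scope to the other.

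**Working it through.** **Inputs from the documents.** 40 endoscopists; 1,918 polyps (2,400 × 0.85 × 0.52 × 1.81 = 1,920, so the count reproduces within rounding); 58% adenomas; ICC 0.05; 50% of subjects per scope; discordant cells from Tables 9-3 to 9-6. **Assumed:** each endoscopist splits cases 50/50 between scopes.

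**Step 1. Sensitivity gain and variance.**
- Gain: CF-HQ190 0.0859 − 0.0365 = 0.0494; PCF-H190 0.0749 − 0.0475 = 0.0274; mean d = 0.0384.
- Per-polyp variance v = b + c − (b − c)²: 0.1200 and 0.1216.
- Adenomas per endoscopist: 1,918 × 0.58/40 = 27.8, or 13.9 per scope.

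**Step 2. True standard error.** Variance of an endoscopist's sum = Σ m·v·[1 + (m − 1) × 0.05] + 2r × 0.05 × m₁m₂√(v₁v₂), where r is the cross-scope correlation. At r = 0 the design effect is 1 + 12.9 × 0.05 = 1.65. The sum's variance is 13.9 × 1.645 × (0.1200 + 0.1216) = 5.53, and SE = √(5.53/27.8²/40) = 0.0134.

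**Step 3. Endoscopist-only bootstrap (comes near the plan's figure).** Power = Φ(0.0384/0.0134 − 1.96) = 81.9%. Specificity power is at least 0.99 in every scenario, so sensitivity decides joint power.

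**Step 4. Endoscopist-then-patient bootstrap, with replacement at both stages.** The bootstrap variance adds the within-operator variance of the mean: 13.9 × 0.95 × 0.2416/27.8²/40 = 0.000103. Bootstrap SE = √(0.000179 + 0.000103) = 0.0168, against a true SE of 0.0134. Power = Φ((0.0384 − 1.96 × 0.0168)/0.0134) = 66.0%. At 2,400 polyps the two SEs are 0.0155 and 0.0126, and power is 73.8%.

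**Step 5. Simulation check.** Dirichlet operator effects and percentile bootstrap; 10,000 trials per scenario, 600 resamples, error about ±1 point. Assumed because the documents do not give them: polyps per patient 1 + Poisson(0.81), and adenoma status independent within patient.

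| Joint power, r = 0 / 0.5 / 1 | Formula | Simulation |
|---|---|---|
| Endoscopist only, 1,918 | 82 / 74 / 67% | 81 / 75 / 69% |
| Endoscopist only, 2,400 | 86 / 78 / 71% | 86 / 78 / 73% |
| Two-stage, 1,918 | 66 / 59 / 53% | 65 / 60 / 56% |
| Two-stage, 2,400 | 74 / 66 / 59% | 74 / 66 / 61% |

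At r = 0, further two-stage simulations with somewhat different settings gave about 64 and 67% at 1,918 polyps and about 73 and 77% at 2,400. That is the source of the quoted ranges.

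**Step 6. No-prediction polyps** (endoscopist-only formula, 1,918 polyps, r = 0). Excluding them (mean prediction rate (0.89 + 0.84)/2 = 0.865) gives 79%; keeping them with aided equal to unaided gives 77%.

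**Step 7. What the effect of assumption 4 depends on** (endoscopist-only formula, 1,918 polyps, r = 0 / 0.5 / 1).
- 80/20 scope mix within endoscopist: 77 / 72 / 68%.
- 90/10 mix: 73 / 70 / 68%.
- One scope per endoscopist: about 67% whatever r is, since the design effect is 1 + 26.8 × 0.05 = 2.34.
- ICC 0.025 with a 50/50 mix: 89 / 85 / 81%.

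With a 50/50 mix and ICC 0.05, across the open readings of polyp count, no-prediction and normal-tissue handling, and bootstrap form, the loss is about 5 to 9 points at r = 0.5 and 9 to 16 at r = 1.

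**The case against.** **The second stage is not specified.** If patients are not redrawn with replacement, the procedure reduces to the endoscopist-only bootstrap, and about 82% is consistent with the stated 80%. This stands as a possibility. However, replacement at both stages is the ordinary meaning of two-level bootstrap resampling, and the text says nothing to displace it.

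**The statistical analysis plan may hold the detail.** Assumption 5 refers to it for the within-subject polyp model, and the revision history records a sample size re-calculation after regulatory feedback. A sensitivity run there cannot be ruled out. If it exists, citing it answers that part.

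**Assumption 4 is disclosed and nothing contradicts it.** This stands. A reader might infer that zero correlation is a mistake and that true power is 67 to 74%. The documents do not support that. They give no estimate of the correlation; 0.5 and 1 are values chosen here. Section 5.3 gives no size and does not mention scopes, and variation between operators is already in the model through the ICC. Nor do 40 endoscopists necessarily act as 80 independent operator-by-scope clusters: that requires everyone to use both scopes, and Table 2-2 asks only for one or more of the two models.

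**Conclusion.** The stated 80% does not follow from the printed inputs and the printed test on its ordinary reading. With assumption 4 left intact, the planned bootstrap gives about 64 to 67% at 1,918 polyps and 73 to 77% at 2,400, so neither polyp count rescues the figure. This rests on replacement at both stages, a 50/50 scope split within each endoscopist and ICC 0.05. The conflict between 48 and 60 predictions per endoscopist stands without any assumption.

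The cross-scope correlation is a secondary point: a sensitivity range on a disclosed, favourable input, and not an error. Its effect shrinks with an uneven scope mix or a lower ICC and vanishes for single-scope operators, whose power is already about 67% because of cluster size.

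A reader might also infer that the final inference is compromised. Assumption 4 does not affect type I error, the decision rule or the final analysis, because resampling whole endoscopists already allows for correlation across scopes. The extra width from the second stage costs power; it does not make the intervals too narrow.

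**What to change.** Rerun the existing simulation with:

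1. the exact planned bootstrap, stating the resampling at each stage;
2. one reconciled polyp count (48 or 60 per endoscopist), corrected in Section 5 and assumption 1 or in Section 9.1.1.2 and the synopsis;
3. a stated scope mix per endoscopist;
4. a stated handling of no-prediction polyps, including whether Tables 9-3 to 9-6 already contain them.

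Replace the single 80% in Section 9.1.1.2 and the synopsis with the rerun's own figure, and report power at cross-scope correlations 0, 0.5 and 1 beside it, labelling assumption 4 as the favourable bound. The figures given here are a check and should not be inserted. If the statistical analysis plan already holds such a run, cite it.

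The cost is one rerun of existing code and probably a less favourable stated power. The correction itself needs no added enrolment.

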### 9.1.2 Secondary Endpoints

1. Number, proportion, unaided NBI prediction and pathology result of diminutive polyps detected by the endoscopist and confirmed by pathology for which CDSD does not return a prediction.
2. Sensitivity, specificity, NPV, PPV of unaided endoscopist prediction using white light compared with pathology.
3. Sensitivity, specificity, NPV, PPV of unaided endoscopist prediction using NBI compared with pathology.
4. Sensitivity, specificity, NPV, PPV of CDS prediction compared with pathology.
5. Sensitivity, specificity NPV, PPV of CDS-aided endoscopist prediction compared with pathology.
6. Number, proportions and pathology results for diminutive polyps with discordant unaided predictions using NBI and aided predictions with CDS.

## 9.2 General Statistical Methods

### 9.2.1 Analysis Sets

Intention to Treat (ITT) analysis will be performed on all subjects meeting the entrance criteria. The primary endpoint will be assessed by ITT analysis on polyp level data.

### 9.2.2 Subgroup Analyses

Subgroup analyses of interest include impact of colonoscopy indication, impact of colonoscope used, impact of endoscopist confidence on sensitivity and specificity, impact of endoscopist experience on level of confidence in prediction, impact of endoscopist experience on frequency with which CDSD returns a result (i.e. influence of endoscope handling) and agreement with pathology as well as unaided and CDSD aided performance segmented by Paris Classification. Additional subgroup analyses may be performed as appropriate.

### 9.2.3 Additional Analyses

In cases where the CDSD-aided endoscopist prediction and the pathology result differs, a recut and reanalysis of the tissue block will be conducted. In such cases, the second successful pathology reading will be recorded and used as the histopathological ground truth.

## 10 Data Management

### 10.1 *Data Collection, Processing, and Review*

Subject data will be recorded in a limited access secure electronic data collection system (EDC). The clinical database will reside on a production server hosted by the EDC System. All changes made to the clinical data will be captured in an electronic audit trail and available for review by the sponsor or its representative. The associated software and database have been designed to meet regulatory compliance for deployment as part of a validated system compliant with laws and regulations applicable to the conduct of clinical studies pertaining to the use of electronic records and signatures. Database backups are performed regularly.

The Investigator provides his/her electronic signature on the appropriate electronic case report forms (eCRFs) in compliance with local regulations. A written signature on printouts of the eCRFs must also be provided if required by local regulation. Changes to data previously submitted to the sponsor require a new electronic signature by the Investigator acknowledging and approving the changes.

Visual and/or electronic data review will be performed to identify possible data discrepancies. Manual and/or automatic queries will be created in the EDC system and will be issued to the site for appropriate response. Site staff will be responsible for resolving all queries in the database.

### 10.2 *Data Retention*

The Principal Investigator or his/her designee or Investigational site will maintain, at the investigative site, all essential study documents and source documentation that support the data collected on the study subjects in compliance with ICH/GCP guidelines. Documents must be retained for at least 2 years after the last approval of a marketing application or until at least 2 years have elapsed since the formal discontinuation of the clinical investigation of

the product. These documents will be retained for a longer period of time by agreement with Olympus or in compliance with other local regulations.

The Principal Investigator or his/her designee will take measures to ensure that these essential documents are not accidentally damaged or destroyed. If for any reason the Principal Investigator or his/her designee withdraws responsibility for maintaining these essential documents, custody must be transferred to an individual who will assume responsibility and Olympus must receive written notification of this custodial change. Sites are required to inform Olympus in writing where paper or electronic files are maintained in case files are stored off site and are not readily available.

## **11 Amendments**

If a protocol revision is necessary which affects the rights, safety or welfare of the subject or scientific integrity of the data, an amendment is required. IRB approval of the revised protocol must be obtained prior to implementation.

## **12 Deviations**

An Investigator must not make any changes or deviate from this protocol, except to protect the life and physical well-being of a subject in an emergency. An investigator shall notify the sponsor and the reviewing IRB of any deviation from the investigational plan to protect the life or physical well-being of a subject in an emergency, and those deviations which affect the scientific integrity of the clinical investigation. Such notice shall be given as soon as possible, but no later than 5 working days after the emergency occurred, or per prevailing local requirements, if sooner than 5 working days.

All deviations from the investigational plan, with the reason for the deviation and the date of occurrence, must be documented and reported to the sponsor. Sites may also be required to report deviations to the IRB, per local guidelines and government regulations.

Deviations will be reviewed and evaluated on an ongoing basis and, as necessary, appropriate corrective and preventive actions (including IRB notification, site re-training, or site discontinuation/termination) will be put into place by the sponsor.

## **13 Device/Equipment Accountability**

The study Devices/equipment shall be securely maintained, controlled, and used only in this clinical study.

The sponsor shall keep records to document the physical location of all study Devices/equipment from shipment of study Devices from Olympus or designated facility/equipment to the investigation sites until return or disposal.

Records shall be kept by clinical sites to document the physical location and conditions of storage of all study Devices/equipment.

The principal investigator or an authorized designee shall keep records documenting the receipt, use, return and disposal of the study Devices/equipment, which shall include the following:

- Date of receipt
- Identification of each study Device/piece of equipment (batch number, serial number or unique code)
- Expiry date, as applicable
- Date or dates of use
- Subject identification
- Date of return (and number) of unused, expired, or malfunctioning study Devices/equipment, if applicable.

## 14 Compliance

### 14.1 *Statement of Compliance*

This study will be conducted in accordance with 21 CFR 812 and 814.20 part 56 and part 50, ISO 14155: Clinical Investigation of Medical Devices for Human Subjects – Good Clinical Practice, the relevant parts of the ICH Guidelines for Good Clinical Practices, ethical principles that have their origins in the Declaration of Helsinki, and pertinent individual country laws and regulations. The study shall not begin until the required approval/favorable opinion from the IRB has been obtained. Any additional requirements imposed by the IRB shall be followed, if appropriate.

### 14.2 *Investigator Responsibilities*

The Principal Investigator of an investigational site is responsible for ensuring that the study is conducted in accordance with the Clinical Trial Agreement, the clinical investigation plan, ISO 14155, ethical principles that have their origins in the Declaration of Helsinki, any conditions of approval imposed by the reviewing IRB, and prevailing local and/or country laws and/or regulations, whichever affords the greater protection to the subject.

The Principal Investigator's responsibilities include, but are not limited to, the following.

- Prior to beginning the study, sign the Clinical Trial Agreement and comply with the Investigator responsibilities as described in such Agreement.
- Prior to beginning the study, sign the Protocol Signature page documenting his/her agreement to conduct the study in accordance with the protocol.
- Provide his/her qualifications and experience to assume responsibility for the proper conduct of the study and that of key members of the site team through up-to-date curriculum vitae or other relevant documentation and disclose potential conflicts of interest, including financial, that may interfere with the conduct of the clinical study or interpretation of results.
- Make no changes in or deviate from this protocol, except to protect the life and physical well-being of a subject in an emergency; document and explain any deviation from the approved protocol that occurred during the course of the clinical investigation.

- Create and maintain source documents throughout the clinical study and ensure their availability with direct access during monitoring visits or audits; ensure that all clinical-investigation-related records are retained per requirements.
- Ensure the accuracy, completeness, legibility, and timeliness of the data reported to the sponsor in the CRFs and in all required reports.
- Record, report to Sponsor, and assess every observed device deficiency.
- Maintain the device accountability records and control of the Device, ensuring that the study Device is used only by authorized/designated users and in accordance with this protocol and instructions/directions for use.
- Allow the sponsor to perform monitoring and auditing activities, and be accessible to the clinical research monitor or auditor and respond to questions during monitoring visits or audit(s).
- Allow and support regulatory authorities and the IRB when performing auditing activities.
- Ensure that informed consent is obtained in accordance with applicable laws, this protocol and local IRB requirements.
- Provide adequate medical care to a subject during and after a subject's participation.
- Inform the subject of any new significant findings occurring during the clinical investigation, including the need for additional medical care that may be required.
- Ensure that clinical medical records are clearly marked to indicate that the subject is enrolled in this clinical study.
- Inform, with the subject's approval or when required by national regulations, the subject's personal physician about the subject's participation in the clinical investigation.
- Ensure that an adequate investigation site team and facilities exist and are maintained and documented during the clinical investigation.
- Ensure that maintenance and calibration of the equipment relevant for the assessment of the clinical investigation is appropriately performed and documented, where applicable.

